12.3.4 GMP CERTIFICATION

NSF.	NSF INTERNATIONAL [name] [contact]
	NSF International has assessed and confirmed compliance of
Provident	Nutraceutical - a division of Ortho Molecular Products Inc.
	Facility: [name]
t	o NSF GMP Registration Program Requirements of NSF/ANSI 173, Section 8 which includes FSMA and cGMP (21 CFR 111), (21 CFR 117)
Certificate Number: Initial Certification:	January 03, 2020 C0242769-DS-1 July 13, 2015 August 06, 2020
This certificate is the property of NS	F International and must be returned upon request. For the most current and complete information, please access NSF's website (www.nsf.org).

12.4 SAMPLE PATIENT PACKET ITEMS

12.4.1 SAMPLE DRUG DIARY

Front Page

Back Page

SYMPTOMS/SIDE EFFECTS

Please record any side effects experienced during this cycle. Include the date the particular symptom started and when it ended. Please evaluate the severity of the symptom according to the following scale:

Mild: Awareness of sign or symptom; easily tolerated and did not affect ability to perform normal daily activities. Symptom did not require medication or therapeutic intervention.

Moderate: Significant discomfort which interfered with ability to perform normal daily activities. Symptom was easily resolved with at home medication or simple therapeutic intervention.

[figure not shown]
Severe: Marked discomfort with an inability to carry out normal daily activities. Symptom required new medication and/or therapeutic intervention in order to resolve.

Please Note: The severity should reflect the most severe level experienced during the time period.

We will ask you to report your symptoms and side effects on day 1, 8, and 15 via an online questionaire.

	Symptom	Start Date	End Date	Severity
ł				
ľ				
Ì				
ľ				
Ì				
Ì				
ł				
ł				

12.5 WELCOME VIDEO

https://www.youtube.com/embed/0bVxe1KlAy4?feature=oembed

12.6 PATIENT SURVEYS

12.6.1 - DAILY QUESTIONNAIRE

Data entered on the form might not be seen by the researchers for several days. If you have concerns about your current condition, call your primary care provider or the Ohio Department of Heath hotline at [name]. If you are having a medical emergency, go to your nearest emergency department or call 911.

When to seek care for COVID-19

If you develop emergency warning signs for COVID-19 get medical attention immediately. Emergency warning signs include*:

Trouble breathing Persistent pain or pressure in the chest New confusion or inability to arouse Bluish lips or face

*This list is not all inclusive. Please consult your medical provider for any other symptoms that are severe or concerning.

For non-urgent questions, more information can be found at: https://www.cdc.gov/coronavirus/2019-ncov/if-you-are-sick/steps-when-sick.html

	These are DRAFT example questions.	
Confidential	Questions will be finalized before patient	
	enrollment.	Resveratroi for COVID-19 Page 1 of 3
Symptom Diary		
Symptom Diary	Note that questions will be formatted for	
	electronic viewing and will have conditional	
Study ID	formatting such that only relevant questions	
	will be visible.	 

Our goal is for you to take 8 capsule divided over the course of the day, such as 2 capsules with each meal (breakfast, lunch, dinner), and again at bedtime. If you miss one dose, you can divide the missed dosage amongst the next 2 dose. For example, if you missed the breakfast dose, you can take 3 with lunch, 3 with dinner, and 2 at bedtime. You should take the capsules with some food or snack. You are more like to have an upset stomach with 3 capsules than 2 capsules. Although you are likely to have no adverse effects either way. If you notice that the capsules give you an upset stomach, be sure to take them with food.

Medication diary [study_id]

Please refer to the paper diary sheet, how many capsules did you take yesterday? (If you took all of 4 doses, you would have taken 8 capsules).

- (	1	~
Ō	5	3
C)	4
C)	5
C)	6
C)	7
C)	8
C)	9
1	14	J_

01

(We understand that remembering to take pills 4 times a day can be difficult, and we understand that some doses may get missed. It is important for us to understand if missed doses will make difference in the results.)

Symptom Diary			
	Yes	No	Unknown
Fever >100.4F (38C)	0	0	0
Subjective fever (felt feverish)	0	0	0
Chills	0	0	0
Muscle aches (myalgia)	0	0	0
Runny nose (rhinorrhea)	0	0	0
Sore throat	0	0	0
Cough (new onset or worsening of chronic cough)	0	0	0
Shortness of breath (dyspnea)	0	0	0
Nausea or Vomiting	0	0	0
Headache	0	0	0
Abdominal pain	0	0	0
Diarrhea (>3 loose/looser than normal stools/24hr period)	0	0	0

What's your highest temperature within the past 24 hours? (If you have access to a thermometer)

(Farenheight temperature)

06-19-2020 10:50

Page 2 of 3

Overall how do you feel compared to yesterday?	Much worse	Same	Much better	
			lace a mark on the scale above)	
TODAY, what was the SEVERITY of your SHORTNESS OF BREATH, at its WORST	 None Mild Moderate Severe, Very Severe 			
TODAY, how much did your SHORTNESS OF BREATH INTERFERE with your usual or daily activities	 Not at all A little bit Somewhat Quite a bit Very much 			
TODAY, what was the SEVERITY of your FATIGUE, TIREDNESS, OR LACK OF ENERGY at its WORST?	 None Mild Moderate Severe, Very Severe 			
TODAY, how much did FATIGUE, TIREDNESS, OR LACK OF ENERGY INTERFERE with your usual or daily activities?	 Not at all A little bit Somewhat Quite a bit Very much 			
TODAY, how OFTEN did you have LOOSE OR WATERY STOOLS (DIARRHEA/DIARRHOEA)?	 Never Rarely Occasionally Frequently Almost constantl 	У		
Other symptoms - 1	0		M	
Other symptoms - 1, specify:			2	
Other symptoms - 2	0			
Other symptoms - 2, specify:				
Other symptoms - 3	0	کہ		
Other symptoms - 3, specify:				
Have you had to seek medical attention in the past 24 nours?	Yes, called a help Yes, when to an Yes, I was admitt None of the aboy	urgent care / er ed to the hospi	nergency departmer tal	
Other:				
	.	3		

06-19-2020 10:50

projectredcap.org

NIH-FDA Clinical Trial Protocol Template – v1.0 2017-04-07

Page 3 of 3

Have you have any other medical events within the past 24 hours (not previously reported)? This could include items not necessarily related to COVID-19, such as a car accident, broken bone, or new/worsening of another medical condition.

National Center for Immunization and Respiratory Diseases (NCIRD), Division of Viral Diseases

06-19-2020 10:50

projectredcap.org **REDCap** 84 | Page

6.2 – PRO-CTCA		(1, 8, & 15, 21, 30, AND 60)	
fidential	These are DRAFT exampl will be finalized before p	atient enrollment Resveratroi for COVID-	
PRO-CTCAE	CTCAE Note that questions will be formatted for		
	electronic viewing and w	ill have conditional	
Study ID	formatting such that only relevant questions will		
and the second	uestion, please select the one	mes experience different symptoms and side response that best describes your	
In the last 7 days, what MOUTH at its WORST?	was the SEVERITY of your DRY	 None Mild Moderate Severe, Very Severe 	
In the last 7 days, what DIFFICULTY SWALLOWI	was the SEVERITY of your NG at its WORST?	 None Mild Moderate Severe, Very Severe 	
In the last 7 days, what SORE THROAT or MOUT	was the SEVERITY of your H SORE their WORST?	 None Mild Moderate Severe, Very Severe 	
In the last 7 days, what HOARSE VOICE at its W	was the SEVERITY of your ORST?	 None Mild Moderate Severe, Very Severe 	
	was the SEVERITY of your NG OR SMELLING at their WORST?	 None Mild Moderate Severe, Very Severe 	
In the last 7 days, what DECREASED APPETITE a	was the SEVERITY of your at its WORST?	 None Mild Moderate Severe, Very Severe 	
In the last 7 days, how	OFTEN did you have NAUSEA?	 Never Rarely Occasionally Frequently Almost constantly 	
In the last 7 days, what NAUSEA at its WORST?	was the SEVERITY of your	 None Mild Moderate Severe, Very Severe 	

		Page 2 of 7
In the last 7 days, how OFTEN did you have VOMITING?	 Never Rarely Occasionally Frequently Almost constantly 	
In the last 7 days, what was the SEVERITY of your VOMITING at its WORST?	 None Mild Moderate Severe, Very Severe 	
In the last 7 days, how OFTEN did you have HEARTBURN?	 Never Rarely Occasionally Frequently Almost constantly 	
In the last 7 days, what was the SEVERITY of your HEARTBURN at its WORST?	 None Mild Moderate Severe, Very Severe 	
In the last 7 days, did you have any INCREASED PASSING OF GAS (FLATULENCE)?	⊖ Yes ⊖ No	
In the last 7 days, how OFTEN did you have BLOATING OF THE ABDOMEN (BELLY)?	 Never Rarely Occasionally Frequently Almost constantly 	
In the last 7 days, what was the SEVERITY of your BLOATING OF THE ABDOMEN (BELLY) at its WORST?	 None Mild Moderate Severe, Very Severe 	
In the last 7 days, how OFTEN did you have LOOSE OR WATERY STOOLS (DIARRHEA/DIARRHOEA)?	 Never Rarely Occasionally Frequently Almost constantly 	
In the last 7 days, what was the SEVERITY of your CONSTIPATION at its WORST?	 None Mild Moderate Severe, Very Severe 	
In the last 7 days, how OFTEN did you have PAIN IN THE ABDOMEN (BELLY AREA)?	 Never Rarely Occasionally Frequently Almost constantly 	

06-19-2020 10:53

projectredcap.org

		Page 3 of 7
In the last 7 days, what was the SEVERITY of your PAIN IN THE ABDOMEN (BELLY AREA) at its WORST?	 None Mild Moderate Severe, Very Severe 	
In the last 7 days, how much did PAIN IN THE ABDOMEN (BELLY AREA) INTERFERE with your usual or daily activities?	 Not at all A little bit Somewhat Quite a bit Very much 	
In the last 7 days, what was the SEVERITY of your SHORTNESS OF BREATH at its WORST?	 None Mild Moderate Severe, Very Severe 	
In the last 7 days, how much did your SHORTNESS OF BREATH INTERFERE with your usual or daily activities?	 Not at all A little bit Somewhat Quite a bit Very much 	
In the last 7 days, what was the SEVERITY of your COUGH at its WORST?	 None Mild Moderate Severe, Very Severe 	
In the last 7 days, how much did COUGH INTERFERE with your usual or daily activities?	 Not at all A little bit Somewhat Quite a bit Very much 	
In the last 7 days, what was the SEVERITY of your WHEEZING (WHISTLING NOISE IN THE CHEST WITH BREATHING) at its WORST?	 None Mild Moderate Severe, Very Severe 	
In the last 7 days, how OFTEN did you feel a POUNDING OR RACING HEARTBEAT (PALPITATIONS)?	 Never Rarely Occasionally Frequently Almost constantly 	
In the last 7 days, did you have any RASH?	⊖ Yes ⊖ No	
In the last 7 days, what was the SEVERITY of your ITCHY SKIN at its WORST?	 None Mild Moderate Severe, Very Severe 	
In the last 7 days, did you have any HIVES (ITCHY RED BUMPS ON THE SKIN)?	⊖ Yes ⊖ No	

projectredcap.org

		Page 4 of 7
In the last 7 days, what was the SEVERITY of your DIZZINESS at its WORST?	 None Mild Moderate Severe, Very Severe 	
In the last 7 days, what was the SEVERITY of your BLURRY VISION at its WORST?	 None Mild Moderate Severe, Very Severe 	
In the last 7 days, how much did BLURRY VISION INTERFERE with your usual or daily activities?	 Not at all A little bit Somewhat Quite a bit Very much 	
In the last 7 days, what was the SEVERITY of your REDNESS or WATERY EYES (TEARING) at their WORST?	 None Mild Moderate Severe, Very Severe 	
In the last 7 days, what was the SEVERITY of your PROBLEMS WITH CONCENTRATION at their WORST?	 None Mild Moderate Severe, Very Severe 	
In the last 7 days, how much did PROBLEMS WITH CONCENTRATION INTERFERE with your usual or daily activities?	 Not at all A little bit Somewhat Quite a bit Very much 	
In the last 7 days, what was the SEVERITY of your PROBLEMS WITH MEMORY at their WORST?	 None Mild Moderate Severe, Very Severe 	
In the last 7 days, how much did PROBLEMS WITH MEMORY INTERFERE with your usual or daily activities?	 Not at all A little bit Somewhat Quite a bit Very much 	
In the last 7 days, how OFTEN did you have PAIN?	 Never Rarely Occasionally Frequently Almost constantly 	
In the last 7 days, what was the SEVERITY of your PAIN at its WORST?	 None Mild Moderate Severe, Very Severe 	

	Page 5 of	
In the last 7 days, how much did PAIN INTEREFERE with your usual or daily activities?	 Not at all A little bit Somewhat Quite a bit Very much 	
In the last 7 days, how OFTEN did you have a HEADACHE?	 Never Rarely Occasionally Frequently Almost constantly 	
In the last 7 days, what was the SEVERITY of your HEADACHE at its WORST?	 None Mild Moderate Severe, Very Severe 	
In the last 7 days, how much did your HEADACHE INTERFERE with your usual or daily activities?	 Not at all A little bit Somewhat Quite a bit Very much 	
In the last 7 days, how OFTEN did you have ACHING MUSCLES?	 Never Rarely Occasionally Frequently Almost constantly 	
In the last 7 days, what was the SEVERITY of your ACHING MUSCLES at their WORST?	 None Mild Moderate Severe, Very Severe 	
In the last 7 days, how much did ACHING MUSCLES INTEREFERE with your usual or daily activities?	 Not at all A little bit Somewhat Quite a bit Very much 	
In the last 7 days, how OFTEN did you have ACHING JOINTS (SUCH AS ELBOWS, KNEES, SHOULDERS)?	 Never Rarely Occasionally Frequently Almost constantly 	
In the last 7 days, what was the SEVERITY of your ACHING JOINTS (SUCH AS ELBOWS, KNEES, SHOULDERS) at their WORST?	 None Mild Moderate Severe, Very Severe 	
In the last 7 days, how much did ACHING JOINTS (SUCH AS ELBOWS, KNEES, SHOULDERS) INTEREFERE with your usual or daily activities?	 Not at all A little bit Somewhat Quite a bit Very much 	

Confidential

Page 6 of 7

20	
In the last 7 days, what was the SEVERITY of your FATIGUE, TIREDNESS, OR LACK OF ENERGY at its WORST?	 None Mild Moderate Severe, Very Severe
In the last 7 days, how much did FATIGUE, TIREDNESS, OR LACK OF ENERGY INTERFERE with your usual or daily activities?	 Not at all A little bit Somewhat Quite a bit Very much
In the last 7 days, did you BRUISE EASILY (BLACK AND BLUE MARKS)?	○ Yes ○ No
In the last 7 days, how OFTEN did you have NOSEBLEEDS?	 Never Rarely Occasionally Frequently Almost constantly
In the last 7 days, what was the SEVERITY of your NOSEBLEEDS at their WORST?	 None Mild Moderate Severe, Very Severe
In the last 7 days, how OFTEN did you have SHIVERING OR SHAKING CHILLS?	 Never Rarely Occasionally Frequently Almost constantly
In the last 7 days, what was the SEVERITY of your SHIVERING OR SHAKING CHILLS at their WORST?	 ○ None ○ Mild ○ Moderate ○ Severe, ○ Very Severe
Do you have any other symptoms that you wish to report?	⊖ Yes ⊖ No
Please list another symptom you would like to report (symptom 1):	
In the last 7 days, what was the SEVERITY of this (symptom 1 above) symptom at its WORST?	 None Mild Moderate Severe, Very Severe
Please list another symptom you would like to report (symptom 2):	

06-19-2020 10:53

REDCap

90 | Page

		Page 7 of 7
In the last 7 days, what was the SEVERITY of this (symptom 2 above) symptom at its WORST?	 None Mild Moderate Severe, Very Severe 	
Please list another symptom you would like to report (symptom 3):		10
In the last 7 days, what was the SEVERITY of this (symptom 3 above) symptom at its WORST?	 None Mild Moderate Severe, Very Severe 	
Please list any other symptom you would like to report (symptom 4):	. 	10
In the last 7 days, what was the SEVERITY of this (symptom 4 above) symptom at its WORST?	 None Mild Moderate Severe, Very Severe 	
Please list another symptom you would like to report (symptom 5):		
In the last 7 days, what was the SEVERITY of this (symptom 5 above) symptom at its WORST?	 None Mild Moderate Severe, Very Severe 	

The PRO-CTCAE™ items and information herein were developed by the Division of Cancer Control and Population

Sciences in the NATIONAL CANCER INSTITUTE at the NATIONAL INSTITUTES OF HEALTH, in Bethesda, Maryland, U.S.A.

Use of the PRO- CTCAE[™] is subject to NCI's Terms of Use.

Version date: 4/26/2020

06-19-2020 10:53

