6.4 STUDY INTERVENTION COMPLIANCE

Participants will document their compliance daily.

Noting that many patients will have a short duration of symptoms (in order to avoid unnecessary side effects), patients will be allowed to discontinue treatment after a minimum of 7 days if they have been symptom free for 3 days. Completion of a minimum of 7 days of treatment whose symptoms have resolved will be consider compliant with treatment.

In case of a single missed dosage, patient will be asked to divide the 2 missed capsules amongst their next 2 dosages. Patient is not to take more than 3 capsules at a time, and no more than 9 capsules in a day.

At the end of the study, participants will report the number of remaining capsules in their bottles at the end of 15 days.

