12.1.3 Certificate of Analysis for Prepared Capsules

Edmont	art Inc. 1 Street NW [name] [name] F [contact]		Analytical Services and Consultation
		REPORT #	90171-2
То	Vita-Age Nutrition	Date	6/24/2020
	[name] T [contact]	Received	2020/06/16

VITA-AGE RESVERATROL; Lot# 20680 (9	0171-2)
-------------------------------------	---------

Test	Specification	Test Result	Method	Analyst	Date	Loc.
Arsenic	N/A	<0.03 ppm	ICP-MS	Hſ	2020/06/23	AB
Cadmium	N/A	<0.02 ppm	ICP-MS	ΗL	2020/06/23	AB
Lead	N/A	2.02 ppm	ICP-MS	ΗL	2020/06/23	AB
Mercury	N/A	<0.02 ppm	ICP-MS	JH	2020/06/23	AB
1. Total Plate Count	N/A	<10 CFU/g	USP <2021/2022>	OM	2020/06/22	AB
2. Yeast & Mold	N/A	<10 CFU/g (Yeast); 600 CFU/g (Mold)	USP <2021/2022>	OM	2020/06/22	AB
3. S. aureus	N/A	Negative	USP <2021/2022>	OM	2020/06/22	AB
4. E. coli	N/A	Negative	USP <2021/2022>	OM	2020/06/22	AB
5. Salmonella	N/A	Negative	USP <2021/2022>	OM	2020/06/22	AB
Resveratrol	500 mg/capsule	460 mg/ 514.17 mg	HPLC-UV	SMC	2020/06/23	AB
		*Based on a unit w	eight of 514.17 mg			

Labs-Mart Testing Locations:

AB - [name]

1. [name] O Prepared by 2020/06/24 Approved by Date [name], Account Manager [name], QC Specialist Raw data are archived by Labo-Mart Inc. Results shown relate only to samples submitted and tested. Labo-Mart Inc. assumes no liability for the use of the results by any party. Testing may be completed at other Labo-Mart Incoations. Statement of conformity only applies to tests currently presented on our scope of accreditation. All required parts of the standard [17025] applicable to a test laboratory are met. Accreditation is location and parameter specific. The tests listed in this report may not be included in the current scope of accreditation. The sample[s] were provided by the customer as listed on this report and therefore results reported apply to the samples as received. Page 1 of 1

This analytical test report shall not be reproduced, except in full, without written permission from Labs-Mart Inc.

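### The draft daily questionnaire gives the missed-dose rule without the limits in section 6.4, so a missed bedtime dose leads to 10 capsules the next day against a cap of 9

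*Combined protocol and SAP*

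**What the plan says.** Section 6.1.2 sets the dose at 2 capsules of 500 mg four times a day. The draft daily questionnaire in section 12.6.1 turns this into a goal of 8 capsules a day, "such as 2 capsules with each meal (breakfast, lunch, dinner), and again at bedtime".

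For a single missed dose, section 6.4 asks the participant to "divide the 2 missed capsules amongst their next 2 dosages" and then sets two limits: "Patient is not to take more than 3 capsules at a time, and no more than 9 capsules in a day".

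The questionnaire gives participants the same split: "If you miss one dose, you can divide the missed dosage amongst the next 2 dose". It adds one worked case: "For example, if you missed the breakfast dose, you can take 3 with lunch, 3 with dinner, and 2 at bedtime". It also warns: "You are more like to have an upset stomach with 3 capsules than 2 capsules". It mentions neither the limit of 3 capsules per intake nor the limit of 9 per day. The form carries the note "These are DRAFT example questions" and is to be finalized before enrollment.

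**The concern.** Participants act on what they are given to read, and the questionnaire is put in front of them every day for 15 days. If its make-up rule can take someone past a maximum that the protocol sets, then doing what the form allows produces a protocol deviation, which section 10.1.10 defines to include noncompliance by the participant.

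The limits have a purpose. Section 4.3 names gastrointestinal side effects as the main constraint on dose, and the questionnaire itself says that 3-capsule intakes are harder on the stomach than 2-capsule ones. At stake is a small tolerability risk and an avoidable deviation. The efficacy analysis is not at stake.

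**Working it through.** **Inputs**
- Full dose: 2 capsules at each of breakfast, lunch, dinner and bedtime, so 4 × 2 = 8 per day (6.1.2 and 12.6.1).
- Make-up rule: the 2 missed capsules are split over the next two doses, one extra capsule at each (6.4 and 12.6.1).
- Limits: 3 capsules per intake and 9 per day (6.4 only).
- Strength: 500 mg by label (6.1.2). The assay line in the certificate of analysis for the prepared capsules (12.1.3) reads "460 mg/ 514.17 mg", that is, 460 mg of resveratrol per capsule.

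**The form's own example.** Missed breakfast: 0+3+3+2 = 8, equal to the daily goal. This reproduces.

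**All four cases, applying the split as the questionnaire words it**

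| Missed dose | That day | Next day | Two-day total | Largest intake |
|---|---|---|---|---|
| Breakfast | 0+3+3+2 = 8 | 2+2+2+2 = 8 | 16 | 3 |
| Lunch | 2+0+3+3 = 8 | 2+2+2+2 = 8 | 16 | 3 |
| Dinner | 2+2+0+3 = 7 | 3+2+2+2 = 9 | 16 | 3 |
| Bedtime | 2+2+2+0 = 6 | 3+3+2+2 = **10** | 16 | 3 |

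A missed dinner dose reaches the cap exactly. A missed bedtime dose is the only case in which both make-up capsules land on the next day, and the only one that passes 9. The per-intake limit is never broken.

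**With the section 6.4 limits applied.** Only the bedtime case changes: the next day becomes 3+2+2+2 = 9 and the two-day total 6+9 = 15. The number of 3-capsule intakes that day falls from 2 to 1.

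**Size of the excess in the resveratrol arm**
- Relative to the cap: 10/9 − 1 = 11%.
- Label strength: 10 × 0.500 = 5.0 g against 9 × 0.500 = 4.5 g, a difference of 0.50 g.
- Assay strength: 10 × 0.460 = 4.60 g against 9 × 0.460 = 4.14 g, a difference of 0.46 g.

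**Meaning of a day.** The count uses calendar days, which fits the form's question about capsules taken the day before. On a rolling count of four consecutive doses, every missed dose would give 3+3+2+2 = 10, including the form's own example. The calendar-day reading is therefore the one that favours the plan.

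**The case against.** The strongest reply is that the form allows 10 capsules but does not require it. Its paragraph opens with a goal of 8 a day, its make-up wording is permissive, and its one example ends at 8. A participant could reasonably take the rule as a way of reaching that day's 8 and start afresh after a missed bedtime dose. That reading is available, but nothing in the text confines the next two doses to the same day, and permission to reach 10 still contradicts a stated maximum of 9.

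Second, section 6.4 is already sound: the split and the limits stand side by side and are best read as a rule with a ceiling. This is right, and no dosing rule in the protocol body has to change.

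Third, the form is a draft, and participants also receive relabelled bottles (6.2.4), a written and video explanation (4.1) and a paper diary (12.4.1). The study label text and the diary's front page cannot be seen, and any of these may carry the cap. This stands as a limit on the finding: it concerns the visible questionnaire text and does not show that participants are misinstructed overall. The questionnaire's answer options for capsules taken are legible only up to 9 and settle nothing either way.

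Fourth, the consequence is close to nil. Section 2.3.1 describes doses up to 5 g as generally well tolerated apart from dose-related gastrointestinal upset, although 2.3.2 words this as single doses and 4.3 records an exception in multiple myeloma. Here 5.0 g would be spread over four intakes of at most 1.5 g. This too is accepted, and it is why the point ranks low.

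**Conclusion.** The point holds. The questionnaire text in 12.6.1 is wrong as written because it leaves out limits that section 6.4 imposes. Following it after a missed bedtime dose gives 10 capsules the next day instead of at most 9.

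This affects one of the four possible missed doses, on one day, by one capsule. It assumes the full dose, all other doses taken, the split used in full and a day counted as a calendar day. The documents do not say how often a bedtime dose is likely to be missed, so the expected number of such days cannot be given. Sample size and the primary analysis are unaffected. It is a minor correction, worth making because it concerns a dosing instruction in a form that is still open.

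**What to change.** Before the questionnaire is finalized, make two additions directly after the split rule:

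1. The limits: *Never take more than 3 capsules in one go, or more than 9 in one day.*
2. A second example: *If you missed the bedtime dose, take 3 with breakfast the next day, then 2 with lunch, 2 with dinner and 2 at bedtime (9 in total). Do not make up the other capsule.*

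The last sentence of the example is an inference from the section 6.4 cap; section 6.4 does not say it in words. Optionally, join the two sentences in 6.4 so that the split is stated to be subject to the limits. The bottle label, diary and video should be checked for the same wording.

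The cost is one sentence and one example in a draft form. Drug supply, sample size and analysis stay as they are.

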1.2 SCHEMA

Prior to Enrollment Screening

•Total n=200

• Review electronic report of newly positive SARS-CoV2 test results of patients 45 and older

- •If old records are available, clinicians to prescreen for exclusion criteria
- •Contact potenially eligible participants by phone to discuss interest in study
- •Patient referred to an online site to review a video discribing the study, risk, benefits.
- Patient given the opportunity to ask questions
- •Obtain informed consent electronically
- •Screen potential participants by inclusion and exclusion criteria
- •Obtain history, document

Randomization

•Intervention Group 1 (n=100)

•Placebo (n=100)

Day1

Baseline Survey & Start treatment

•Patient take Vitamin D3 100,000 IU on day and starts treatment or placebo

• Patients will receive an baseline assessment using Patient-Reported Outcomes version of the Common Terminology Criteria for Adverse Events (PRO-CTCAE[™]).

Day 2-15

Treatment or placebo and daily online survey

•Participant to take 2 capsules of intervention or placebo 4 times per day for 15 days.

• Participant will receive a daily online survey to assess for signs and symptoms of COVID-19 and to report potential side effects. If a patient has not completed an online survey within 24 hours, the patient will be contacted via phone to check their status.

Day 8, 15, 21

Weekly PRO-CTCAE Survey

•Patients will questionnaire with 7 day look back of adverse events based on the Patient-Reported Outcomes version of the Common Terminology Criteria for Adverse Events (PRO-CTCAE[™]).

Between day 21-30 Follow-up assessments for efficacy

•Clinicians will perform a chart review to assess patient outcomes as well as contact patient for an exit interview via phone.

Day 30 and Day 60

Long term assesment

[figure not shown]
• Participant Completes PRO-CTCAE to evaluate for adverse events

Study Completion Follow-up assessments of study endpoints and safety

•Data analysis

• Possible long term follow up of adverse events as outlined in section 8.3

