Participant Monitoring and Follow-up: Starting on day 1, and continuing daily for 15 days, subjects will be contacted via e-mail or text message (according to the subject's preference. Messages will include a reminder to take their study medication as scheduled and complete the daily survey (see appendix 12.6.1) each evening prior to going to bed. Subjects will be asked to complete a short questionnaire covering: 1) symptoms they had that day that may be related to COVID-19 (e.g., fever, cough, dyspnea), their frequency and severity; 2) report any other related or non-related medical events; 3) any medications they have taken to relieve symptoms, or other new medications they have not previously reported to study personnel; and 4) any visits they have made to healthcare providers, outpatient centers or hospitals, and details regarding those visits. Subjects will be reminded to contact their primary care physician if they experience symptoms that are worsening or that are concerning to them. For any such contact, they should inform their physician or other healthcare provider that they are enrolled in a clinical trial involving a dietary supplement.

Participants with complete on online PRO-CTCAE questionnaire on days 1, 8 (+1 day), 15 (+1 day), 21 (+1 day), 30, and 60 to monitor for adverse events.

Subjects who do not complete questionnaires will receive a reminder Xe-mails. All patients will be called for a phone interview after 21 days. If subjects cannot be contacted via phone, study personnel will attempt to contact the spouse/family member/friend who is listed as the secondary contact in order to determine the subject's status. A subject will be considered lost to follow-up if their status concerning hospitalization during the study period cannot be verified.

Outcome Assessment and Other Key Variables. Hospitalizations will be determined based on query of subject and/or the subject's secondary contact. The subject's medical records will be requested from the admitting hospital (and discharging hospital, if separate) via a HIPAA authorization.

Additional outcomes will include assessing number of days with fever and to assess symptoms, including dyspnea and fatigue. Questionnaires to assess symptoms will be based on the PRO-CTCAE (see appendix 12.6) (National Cancer Institute, 2020).

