8.3.4 TIME PERIOD AND FREQUENCY FOR EVENT ASSESSMENT AND FOLLOW-UP

The occurrence of an adverse event (AE) or serious adverse event (SAE) may come to the attention of study personnel by way of participant online survey results and interviews of a study participant presenting for medical care, or upon review by a study monitor.

All AEs including local and systemic reactions not meeting the criteria for SAEs will be captured on the appropriate case report form (CRF). Information to be collected includes event description, time of onset, clinician's assessment of severity, relationship to study product (assessed only by those with the training and authority to make a diagnosis), and time of resolution/stabilization of the event. All AEs occurring while on study must be documented appropriately regardless of relationship. All AEs will be followed to adequate resolution.

Any medical condition that is present at the time that the participant is screened will be considered as baseline and not reported as an AE. However, if the study participant's condition deteriorates at any time during the study, it will be recorded as an AE.

Changes in the severity of an AE will be documented to allow an assessment of the duration of the event at each level of severity to be performed. AEs characterized as intermittent require documentation of onset and duration of each episode.

Research clinicians will record all reportable events with start dates occurring any time after informed consent is obtained until 7 (for non-serious AEs) or 30 days (for SAEs) after the last day of study participation. At each study visit, the investigator will inquire about the occurrence of AE/SAEs since the last visit. Events will be followed for outcome information until resolution or stabilization.

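### The two event-capture items on the draft daily questionnaire look back only 24 hours, so non-hospital care visits and non-symptom medical events on a missed survey day are not asked about on the next form

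*Combined protocol and SAP*

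**What the plan says.** Section 4.1 has participants surveyed by e-mail or text: "Starting on day 1, and continuing daily for 15 days". Among the topics the questionnaire is to cover are medical events, whether related or not, and "any visits they have made to healthcare providers, outpatient centers or hospitals, and details regarding those visits". Section 8.3.4 sets the standard for safety data: "All AEs occurring while on study must be documented appropriately regardless of relationship".

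The draft form in Appendix 12.6.1 puts this into two items. The care-seeking item begins "Have you had to seek medical attention in the past 24" and is completed by the word for hours. The other item reads "Have you have any other medical events within the past 24 hours (not previously reported". Both have the same one-day window. In the second, the words about earlier reporting sit inside that window and do not widen it.

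For missed surveys, Section 1.2 says: "If a patient has not completed an online survey within 24 hours, the patient will be contacted via phone to check their status". Section 5.5 also provides for both reminder e-mails and calls to non-responders; Section 4.1 mentions reminder e-mails at that point. The form itself is provisional: "These are DRAFT example questions", to be finalized before enrollment.

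**The concern.** Section 4.1 describes what the survey should capture without limiting it to days on which a form is completed, and Section 8.3.4 covers all AEs on study. The form is narrower. With a fixed 24-hour window, any day without a completed form is a day about which these two items never ask, and nothing on the next form goes back to it.

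The data at stake are outpatient, urgent-care and emergency visits that do not lead to admission, and medical events that are not symptoms, such as an injury or the worsening of another condition. The trial obtains no laboratory studies (Section 4.1), and Section 8.3.1 names online questionnaires and exit interviews as the AE sources, so the wording of the form matters more than it would in a trial with clinic visits. Section 8.3.4 also asks for onset and resolution times, and those are harder to establish weeks later.

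**Working it through.** The plan states no figure on this point, so there is none to reproduce. The check compares the form with the other capture routes and then gives an illustration.

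**Step 1. One case followed through the instruments.** A participant completes no form on days 5, 6 and 7, goes to urgent care on day 6 without being admitted, and answers truthfully on the evening of day 8.

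| Route | Asks about the day-6 visit? |
|---|---|
| Daily form, day 8 (12.6.1) | No. The window reaches back to the evening of day 7. |
| PRO-CTCAE, day 8 (4.1, 12.6.2) | The 7-day look-back covers symptoms on days 5 to 7, with free-text symptom slots. No item shown asks about care visits or non-symptom events. |
| Paper diary (12.4.1) | The page shown records side effects with start and end dates. It has no field for visits. |
| Call after a missed survey (1.2, 5.5) | Possibly. The stated purpose is a status check; nothing says the two items are re-asked for the missed day or that the answers are entered. |
| AE inquiry since the last visit (8.3.4) | In general terms, for AEs. Contacts in this trial are largely remote, and no visit is scheduled in the first three weeks. |
| Interview and chart review, days 21 to 30 (1.2, 4.1) | Yes, in principle. Recall is then 21 − 6 = 15 to 30 − 6 = 24 days. |

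An admission on day 6 would also be missed by the day-8 daily form. It has separate routes, however: query of the participant or secondary contact with hospital records (Section 8.1), and medical record review for the endpoints (Sections 9.4.2 and 9.4.3).

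**Step 2. Size at the level of the form (illustration).** Inputs from the documents: 200 participants and 15 survey days, so 200 × 15 = 3,000 scheduled survey-days. Assumed: each day is missed independently with probability m, from 5% to 30%, and events are spread evenly over the 15 days.

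- Under the 24-hour wording, an event-day is unasked if its own form is missed. The unasked share is m.
- Under a look-back to the last completed survey, an event on day d is unasked only if every form from day d to day 15 is missed. The unasked share is (1/15) × (m + m² + … + m¹⁵), which is very close to m / [15(1 − m)].

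| m (assumed) | Survey-days missed of 3,000 | Unasked, 24-hour wording | Unasked, since last survey |
|---|---|---|---|
| 5% | 150 | 5% | (0.05/0.95)/15 = 0.35% |
| 10% | 300 | 10% | (0.10/0.90)/15 = 0.74% |
| 20% | 600 | 20% | (0.20/0.80)/15 = 1.7% |
| 30% | 900 | 30% | (0.30/0.70)/15 = 2.9% |

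**Step 3. If missing a form is linked to the event.** Suppose the form is missed on a share q of event-days and on a share m of later days. The unasked share is q now, and q × (1 + m + … + m¹⁴)/15 on average after the change. With q = 50%, it falls from 50% to 0.50 × 1.111/15 = 3.7% at m = 10%, and to 0.50 × 1.429/15 = 4.8% at m = 30%.

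These are shares of days that the two items fail to ask about. They are not counts of lost events: the documents give no event rate, and calls and interviews will recover some.

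**The case against.** The best case on the other side is that the daily form is one instrument among several. The 7-day PRO-CTCAE on days 8, 15 and 21 covers symptoms on missed days, the paper diary dates side effects, and a missed survey triggers a call in which a recent emergency visit would probably come up. Outpatient visits are not an endpoint. The form is a draft, and it warns that entries might not be seen for several days, so it was not built as an early-warning tool. A sentence in Section 4.1 about outpatient visits and hospitalizations over the 60-day period is damaged in the available text, so a further reporting or authorization route cannot be excluded.

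Most of this stands, and it confines the point to care visits and non-symptom events. It does not remove the point: in the text available, no route is instructed to re-ask the two items for the missed day before the interview.

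A reader might infer two stronger conclusions.

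- *Primary-endpoint hospitalizations are lost.* The documents do not support this. Sections 9.4.2 and 9.4.3 establish the primary and secondary endpoints by medical record review.
- *The sickest participants are the likeliest to miss forms, so the loss is informative.* This is plausible, but no passage says who misses surveys or how often. The gap exists whoever misses them.

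Nor are missed days unasked on every form, because the PRO-CTCAE asks about their symptoms.

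**Conclusion.** The point holds in a narrow form. Both event-capture items stop at 24 hours, so non-hospital care visits and non-symptom medical events on missed survey days are not asked about on the next daily form, and the PRO-CTCAE items shown do not fill the gap. What suffers is the completeness, dating and timeliness of AE and outpatient-care data. The efficacy analyses are not threatened.

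The form-level loss equals the missed-day rate, whatever that proves to be. Over an assumed 5% to 30%, a since-last-survey look-back would bring it down to about 0.35% to 2.9%. The percentages rest on assumed rates, independent misses and evenly spread events; the comparison of the instruments needs none of these. Minor to moderate priority.

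**What to change.** When the form in 12.6.1 is finalized, replace the 24-hour phrase in both items with 'since you last completed this survey on [auto-filled date]'; on day 1 use 'since you joined the study'. Add an event-date field that opens when the answer is yes.

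The cost is two wording changes, one piped date and one conditional field in REDCap. The downside is slightly longer recall after missed days. Runs of missed days at the end of the 15-day survey period remain uncovered by the form, as do days 16 onward, when it is no longer sent; for these the interview after day 21 remains the route.
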